2.2 Secondary objective(s)

- To describe the baseline demographic and clinical characteristics, as well as pharmacological and device treatment of CHF patients managed in the primary care setting (in the total population of enrolled patients and also sub-grouped into different European country and patient characteristics clusters).
- To assess in clinically stable patients the impact of patients' key baseline characteristics on the cardiologists' and primary care physicians' prescription practice for HF treatment and the adherence of these treatment choices to the recommendations of the current ESC guidelines.

- To describe the blood levels of NT-proBNP in CHF patients managed in the primary care setting.
- To describe the proportion of CHF patients managed in the primary care setting considered as being clinically stable according to the above definition ([Section 2.1](#)).
- To describe local prescription practice of cardiologists for the treatment of clinically stable CHF patients with NT-proBNP levels ≥ 600 pg/ml.
- To describe local prescription practice and decision making of primary care physicians for the treatment of clinically stable CHF patients with NT-proBNP levels ≥ 600 pg/ml.
- To characterize how treatment optimization, defined as prescription of treatment regimens adherent to the recommendations of the ESC guidelines affects NT-proBNP levels in clinically stable CHF patients with baseline NT-proBNP levels ≥ 600 pg/ml.
- To assess the baseline health-related quality of life (QoL) in CHF patients and describe the temporal course of QoL after specialist referral in clinically stable CHF patients with NT-proBNP ≥ 600 pg/ml by means of EuroQol EQ-5D and KCCQ questionnaires.

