5.6.4 Early study termination by the sponsor

The study can be terminated by Novartis at any time for any reason. This may include reasons related to practical issues, or for regulatory or medical reasons (including slow enrolment). Should this be necessary, the patient must be seen as soon as possible and treated as a prematurely withdrawn patient. The investigator may be informed of additional procedures to be followed in order to ensure that adequate consideration is given to the protection of the patient's interests. The investigator will be responsible for informing the Institutional Review Board/Independent Ethics Committee (IRBs/IECs) of the early termination of the trial.

6 Visit schedule and assessments

The study comprises 3 visits: baseline (Visit 1), Visit 2 (recommended max. 6 months after baseline), Visit 3 (recommended at least 3 months and preferably not later than 4 months after Visit 2; max. 10 months after baseline). At baseline (Visit 1) all consecutive CHF patients who satisfy all inclusion and exclusion criteria should be documented and should complete the QoL questionnaires. At this visit, the investigator will assess whether the patient's status is considered clinically stable (as defined in [Section 2.1](#)) and document his/her decision. Thereafter all patients will undergo blood-sampling for on-site NT-proBNP measurement. Only patients considered clinically stable and with NT-proBNP levels ≥ 600 pg/ml will be referred to a cardiologist for evaluation of treatment optimization. After the visit to the cardiologist, but no later than 6 months after the baseline visit, the patient should return to the investigator's office for Visit 2. At Visit 2, the patient should complete the QoL questionnaires and the cardiologist's recommendations will be reviewed and documented by the investigator; at this visit, the investigator should document, if the cardiologist's recommendations or changes for the patient's HF-treatment will be followed or continued, respectively. The investigator should provide reasons if the recommendations are not followed and document the prescribed HF treatment. At Visit 3, maximally 10 months after baseline, but no earlier than 3 months after Visit 2, the patient should return for the final visit, where clinical and QoL outcomes will be documented and thereafter the patient will undergo blood sampling for measurement of NT-proBNP levels.

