6.2 Patient demographics/other baseline characteristics

Patient demographic and baseline characteristic data to be collected on all patients/subjects include: year of birth, age, sex, race, living conditions, employment status, education level and smoking status, HF etiology, medical history/current medical conditions that were present before signing informed consent where possible, diagnoses and not symptoms will be recorded. Furthermore, where allowed by local laws and regulations, information on health insurance status will be collected. In addition, HF-hospitalization history and emergency room (ER) admissions due to HF over the last 12 months prior to baseline will be recorded.

The investigator will document for all patients their current HF treatment, including drug- and non-drug treatments, as well as any concomitant medication for non-HF indications.

Investigators will have the discretion to record abnormal test findings on the medical history CRF whenever in their judgment, the test abnormality occurred prior to the informed consent signature.

At baseline all patients will be asked to complete two QoL questionnaires (EQ-5D and KCCQ).

Thereafter the investigator will document if he/she sees the patient as being clinically stable, i.e. the patient currently does not require and, in the last 3 months prior to the baseline visit has not had, any change in his/her pharmacological or device treatment of HF.

All patients will have a venous blood sample taken for on-site measurement of NT-proBNP; please note that this measurement should only be performed after the decision regarding the clinical stability of the patient's status is made and documented.

Only patients considered clinically stable as per above definition by the investigator and with NT-proBNP levels ≥ 600 pg/ml will be referred to a cardiologist for evaluation for treatment optimization.

Patients, who are considered not clinically stable according to the above definition or show NT-proBNP levels < 600 pg/ml will not continue in the prospective period of the study – i.e. only baseline information will be documented for these patients.

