9.1 Analysis sets

Analysis of baseline variables will be carried out on all patients who signed the study information consent (Enrolled Set).

Analysis regarding the prospective period of the study will be carried out on all patients entering into this study period – the respective patient set will be labeled Follow-up Set.

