knowledge, and QoL. The following KCCQ domains will be calculated for this study: physical limitation, symptom stability, symptom frequency, symptom burden, self-efficacy, QoL, and social limitation. Each subscore is transformed to a 0–100 scale, with higher score indicating higher level of functioning. A score of 100 represents perfect health whereas a score of 0 represents the worst condition. A clinical summary score is built by the mean of the physical limitation and total symptom scores. The total symptom score is calculated as the mean of the symptom frequency and symptom burden scores. Below are the calculation rules for each score:

- Physical Limitation. Physical Limitation Score = $100 * [(\text{mean of questions 1a-f actually answered}) - 1] / 4$
- Symptom stability
 - If question 2 was answered with 6 (=no symptoms over the last 2 weeks) this will be transferred to 3 (=not changed).
 - Symptom stability score = $100 * [(\text{Question 2}) - 1] / 4$
- Symptom frequency. Symptom Frequency is computed based on the following standardization:
 - $S3 = [(\text{Question 3}) - 1] / 4$
 - $S5 = [(\text{Question 5}) - 1] / 6$
 - $S7 = [(\text{Question 7}) - 1] / 6$
 - $S9 = [(\text{Question 9}) - 1] / 4$;
 - Symptom frequency score = $100 * (\text{mean of } S3, S5, S7 \text{ and } S9)$
- Symptom burden. Symptom burden score = $100 * [(\text{mean of questions 4, 6 and 8 actually answered}) - 1] / 4$
- Self-efficacy. Calculated as = $100 * [(\text{mean of questions 10 and 11}) - 1] / 4$
- QoL. Calculated as $100 * [(\text{mean of questions 12, 13 and 14 actually answered}) - 1] / 4$
- Social limitation. Calculated as $100 * [(\text{mean of questions 15a to 15d actually answered}) - 1] / 4$
- Total symptom score = mean of the following available summary scores:
 - Symptom frequency score
 - Symptom burden score
- Clinical summary score = mean of the following available summary scores:
 - Physical limitation score
 - Total symptom score

5 Analysis data sets

Only patients for whom all core Baseline characteristics are available will be included in the final analysis; core Baseline characteristics are defined as: gender, year of birth, NT-proBNP.

For all patients fulfilling these selection criteria, the following analysis sets will be defined:

- Analysis of Baseline variables will be carried out in all patients who signed the study information consent (Enrolled Set).

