7.2 Disposition of patients

Analysis of patient dispositions will be performed without stratifications described in [Section 7.1](#).

The following variables will be analysed in terms of frequency distributions describing the disposition of patients in this study:

- Number of patients in the analysis sets overall and by country (all patients)

- Protocol deviations (Enrolled Set and Follow-up Set)
- Number of patients violating inclusion and exclusion criteria (for each criterion; Enrolled Set, Follow-up Set)
- Number of patients with premature study discontinuation (Follow-up Set)
- Reasons for premature study discontinuation overall (patients with preliminary study discontinuation)

In addition, the variables at Visit 1 for *NT-proBNP, stability and suitability for prospective interventional period* (as described in [Section 6.2](#)) will be summarised without further stratification as follows:

- NT-proBNP ever tested before Visit 1 (Enrolled Set)
- NT-proBNP in groups (< 600 pg/ml, \geq 600 pg/ml) at Visit 1 (Enrolled Set)
- Clinical stability of the patient (Enrolled Set)
- Suitability for prospective interventional period of the study (Enrolled Set)
- Referral to cardiologist (Enrolled Set – patients suitable for prospective period)

The reasons for non-referral to cardiologist will be listed by patient.

The time between Visit 1 and Visit 2 and the time between Visit 2 and Visit 3 will be summarized for the Follow-Up Set.

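### SAP section 5 narrows the protocol's Enrolled Set to patients with sex, year of birth and NT-proBNP recorded, and SAP section 7.13 does not declare the change

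*SAP*

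**What the plan says.** The protocol sets no completeness condition. Section 9.1 states: "Analysis of baseline variables will be carried out on all patients who signed the study information consent (Enrolled Set").

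SAP section 5 opens with a restriction: "Only patients for whom all core Baseline characteristics are available will be included in the final analysis". It specifies that "core Baseline characteristics are defined as: gender, year of birth, NT-proBNP". The sets come only after that: "For all patients fulfilling these selection criteria, the following analysis sets will be defined". The Enrolled Set is then described in the protocol's terms, as the patients who gave consent, although the filter has already been applied.

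Three other places matter:

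- **Objective.** Protocol section 2.2 includes: "To describe the proportion of CHF patients managed in the primary care setting considered as being clinically stable". SAP section 7.2 tabulates "Clinical stability of the patient (Enrolled Set"), so it uses the filtered set.
- **Order of events at Visit 1.** Protocol section 6.2 says of NT-proBNP that "this measurement should only be performed after the decision regarding the clinical stability" has been made and documented. A stability record can therefore exist without a test result.
- **Declared deviations.** SAP section 7.13 lists three: HF medication analysed by visit, the A1/A2 cross-table split up, and fewer country-stratified treatment analyses. The core-data filter is not one of them, and SAP section 2.5 says that the SAP agrees with the protocol.

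**The concern.** Two analysis sets carry the same name and the same description but have different members. A reader of the report would take the Enrolled Set to be the protocol's set.

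The filter also removes patients from analyses that need none of the missing values. The stability proportion requires only the physician's judgement. Baseline HF treatment, clinical features, vital signs and quality of life do not require NT-proBNP either. The study intends to document consecutive eligible patients so as to describe primary-care practice, and losing consented patients for lack of one test result works against that.

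At stake is the stable proportion, which can be biased if the patients without a result differ in stability from those with one, together with the transparency of the Visit 1 denominators.

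**Working it through.** **1. The plan's own figures.** Protocol section 9.8 requires 2,160 patients in the prospective period and assumes that 60% have NT-proBNP ≥ 600 pg/ml: 2,160 / 0.60 = 3,600. With 10% dropout, 3,600 / 0.90 = 4,000, and 4,000 × 0.60 = 2,400. These reproduce exactly. None of them allows for missing core data, so the plan has no figure for the filter's effect.

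**2. Inputs the documents do not give (assumed).**

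- m, the share of consented patients removed by the filter: 1% to 10%.
- p_complete, the stable proportion among those kept: 80% for illustration.
- p_missing, the stable proportion among those removed: 20 points lower, with 0% and 100% as extremes.

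**3. Formula.** Over all consented patients,

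p_all = (1 − m) × p_complete + m × p_missing.

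The filtered analysis reports p_complete, so

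bias = p_complete − p_all = m × (p_complete − p_missing).

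**4. Results**, with counts on the planned 4,000:

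| m | Removed | Bias if stability is 20 points lower | p_all at p_complete = 80%, p_missing from 0% to 100% |
|---|---|---|---|
| 1% | 40 | 0.01 × 20 = 0.2 points | 79.2% to 80.2% |
| 2% | 80 | 0.02 × 20 = 0.4 points | 78.4% to 80.4% |
| 5% | 200 | 0.05 × 20 = 1.0 point | 76.0% to 81.0% |
| 10% | 400 | 0.10 × 20 = 2.0 points | 72.0% to 82.0% |

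The third column does not depend on p_complete. If p_missing equals p_complete, the bias is zero at every m. The last column shows that either sign is possible: at the extremes, the filtered figure overstates by 0.8 to 8.0 points or understates by 0.2 to 2.0 points.

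**5. Scale.** The 95% half-width for a proportion of 80% is 1.96 × √(0.8 × 0.2 / 4,000) = 1.2 points, and 1.3 points with 10% removed (n = 3,600). Under the 20-point assumption, the bias is below sampling error at 5% removed and above it at 10%. SAP section 4.2 reports that recruitment stopped early. A smaller sample would widen the interval; the bias in points depends only on m and the difference in stability.

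**6. Reach.** Protocol section 6 states: "Only patients considered clinically stable and with NT-proBNP levels ≥ 600 pg/ml will be referred to a cardiologist for evaluation of treatment optimization". A patient in the Follow-up Set should therefore have a result. The NT-proBNP condition can remove such a patient only if referral happened without one; otherwise only a missing sex or birth year could. The primary analysis is in the Follow-up Set, and so are the adverse event incidence tables (SAP section 7.9.1).

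**The case against.** The strongest reply is that little will be missing and that a minimum valid record is a reasonable requirement. Protocol section 3.1 requires the test in stable and unstable patients alike, on site with a handheld device. Protocol sections 8.1 and 8.2 provide monitoring and automatic completeness checks, and SAP section 2.5 adds cleaning before the final analysis. SAP section 7.2 counts set sizes over all patients, so the number removed may be visible. The study is described as exploratory, and only Visit 1 descriptions are materially exposed.

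Most of this stands. It argues for a small effect and against any claim about the primary analysis. It does not explain why the set differs from the protocol's without being declared, and the set counts are not planned by stability status.

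A reader might go further and infer that the filter does inflate the stable proportion: an unstable patient cannot enter the prospective period whatever the result, so the test may be skipped more often in that group. The route is plausible for deliberate skipping, which would itself be a protocol deviation. It does not follow for failed strips or samples, and no document links missing results to stability.

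The size depends heavily on what is assumed. Let S be the true stable proportion, 75% for illustration, and u and s the missing shares in unstable and stable patients. The reported figure is S(1 − s) / [S(1 − s) + (1 − S)(1 − u)]:

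- u = 10% to 30%, s = 0: 76.9% to 81.1%.
- u = 10%, s = 5%: 0.7125 / 0.9375 = 76.0%.
- u = 5%, s = 2%: 0.7350 / 0.9725 = 75.6%.
- u = s: 75.0%, no bias.

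The first range rests on no missing results at all in stable patients, which nothing in the documents supports.

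**Conclusion.** The textual defect is established and needs no assumption: SAP section 5 narrows the protocol's Enrolled Set, keeps the old description, and leaves the change out of section 7.13. Valid stability judgements and other Visit 1 data are dropped for want of a variable that their analysis does not use.

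The statistical consequence is conditional. The stable proportion can be biased if missingness is related to stability, by m × (p_complete − p_missing). That is zero if they are unrelated, and 0.2 to 2.0 points too high if 1% to 10% are removed and stability is 20 points lower among them. Both inputs are assumed, and the documents fix neither size nor direction.

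It would be wrong to read the filter as damaging every analysis. The NT-proBNP condition leaves the primary analysis essentially unaffected. This is a minor point, worth correcting because correction is cheap.

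**What to change.** In SAP section 5, remove the core-data condition and define the Enrolled Set as all patients who gave consent, as in Protocol section 9.1. Handle a missing sex, birth year or NT-proBNP variable by variable: a missing birth year then affects only age tables, and a missing NT-proBNP only tables that use it. SAP section 7.1 already bases percentages on the observed data for each parameter, so no new rule is needed. Add to SAP section 7.2 the number missing for each core variable, by stability status.

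If the sponsor prefers to keep the filter, list it in SAP section 7.13 with the reason, correct the description of the Enrolled Set, report the number removed by reason, and show the stable proportion with and without the filter.

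The cost is SAP wording and one or two table changes. The downside is that denominators will differ slightly between Visit 1 tables, which the missing counts already planned for quantitative variables and a footnote can explain.

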6.1 Variables with respect to the primary objective

The variables used for the primary analysis are the assessment of the patient's treatment at Baseline (A1) and the assessment of the patient's treatment at Visit 2 (A2) with respect to the adherence to the current ESC guidelines (level 1 and level 2 as described in [section 4.5.1](#)). In addition, the guideline adherence at Visit 3 will be assessed (A3).

6.2 Variables with respect to the secondary objectives

Demographics

- Age (in years)
- Age in groups (< 65, ≥ 65 to < 75, ≥ 75 to < 85, ≥ 85 years)
- Gender (Male, Female)
- Race (Caucasian, Black, Asian, Other). If "Other": Specification
- Living characteristics (Living independently in household (alone), Living independently in household (with spouse or significant other), Living in residence with family member (non-spousal or significant other), Living in a long term care facility, Transient housing)
- Environmental living situation (Urban, Suburban, Rural)
- Health insurance status (Statutory health insurance, Private health insurance, Combination of statutory and private health insurance, None)
- Highest educational level (Primary education, Secondary education, University, None)
- Employment status (Student, Employed (part time), Employed (full time), Homemaker, Retired, Unemployed, Sustained sick leave)
- General smoking status (Never, Former, Current)
- Consumption of cigarettes (Never, Former, Current).
 - If "Former" or "Current": amount of consumption in pack years.
- Consumption of electronic cigarettes (Never, Former, Current).
 - If "Former or Current": Duration of consumption (in years).
- Consumption of cigars (Never, Former, Current)
 - If "Former or Current": Duration of consumption (in years).

- Consumption of pipes (Never, Former, Current).
 - If “Former or Current”: Duration of consumption (in years).
- Consumption of chewing tobacco (Never, Former, Current).
 - If “Former or Current”: Duration of consumption (in years).
- Consumption of nicotine patches (Never, Former, Current).
 - If “Former or Current”: Duration of consumption (in years).
- Consumption of other tobacco products (Never, Former, Current).

Clinical features (Visit 1)

- Primary etiology of HF (Ischemic, Non-Ischemic).
- Primary etiology of HF if “Non-Ischemic” (Hypertensive, Diabetic, Alcoholic, Viral cardiomyopathy, Infectious cardiomyopathy, Peripartum, Drug induced, Cardiac arrhythmia, Valvular disease, Other). If “Other”: Specification
- Duration of HF (in years)
- Duration of HF in categories (> 3 years, ≤ 3 years).
- Any hospitalization due to HF in the last 12 months (Yes, No)
- Any visit of emergency room (without hospitalization) due to HF in the last 12 months (Yes, No)
- Any visit of an HF outpatient clinic or a cardiologist due to HF in the last 12 months (Yes, No)
- Performance of diagnostic procedures: Echocardiogram, Electrocardiogram, Chest X-ray, Pulmonary function test, Computed tomography of the heart, Cardiac MRI, Cardiac catheterization, Coronary angiography, 6-minute walking test, Laboratory test
- Left ventricular ejection fraction (LVEF, in %)
- Performance of therapeutic procedures: Percutaneous coronary intervention, Coronary artery bypass graft surgery, Carotid stent, Valve surgery, Cardiac resynchronisation therapy device, Cardiac resynchronisation therapy device – pacemaker, Cardiac resynchronisation therapy device – Implantable cardioverter defibrillator with pacing capabilities, Implantable cardioverter defibrillator, Left ventricular assist device, Ultrafiltration, Heart transplantation, Other. If “Other”: Specification.
- Concomitant disease:
 - Atrial fibrillation, Atrial flutter, Tachyarrhythmia, Diabetes mellitus Type 1, Diabetes mellitus Type 2, Obesity, Stable angina pectoris, Unstable angina pectoris, Asthma, Anemia, Depression, COPD, Renal disease – due to Hypertension, Renal disease – due to diabetes, Renal disease – Other, Hypertension, Carotid artery stenosis, Renal artery stenosis, Dyslipidemia, Primary hyperaldosteronism, Hyperthyroidism, Hypothy-

reoidism, Peripheral vascular disease, Sleep apnea, Parkinson's disease, Alzheimer's disease, Peripheral neuropathy (any etiology), Dementia (other than Alzheimer's), Rheumatoid arthritis, Osteoporosis, Alcoholic liver disease, B chronic hepatitis, C chronic hepatitis, Steatohepatitis (Absent, Present)

- History of myocardial infarction, Prior stroke, Prior transient ischemic attack, History of venous thromboembolism, History of angioedema, Previous/current malignant disease (Yes, No)
- Other comorbidity (Yes, No). If Yes: Specification.

Clinical features (Visit 2 and 3)

- Concomitant disease:
 - Atrial fibrillation, Atrial flutter, Tachyarrhythmia, Diabetes mellitus Type 1, Diabetes mellitus Type 2, Obesity, Stable angina pectoris, Unstable angina pectoris, Asthma, Anemia, Depression, COPD, Renal disease – due to Hypertension, Renal disease – due to diabetes, Renal disease – Other, Hypertension, Carotid artery stenosis, Renal artery stenosis, Dyslipidemia, Primary hyperaldosteronism, Hyperthyroidism, Hypothyroidism, Peripheral vascular disease, Sleep apnea, Parkinson's disease, Alzheimer's disease, Peripheral neuropathy (any etiology), Dementia (other than Alzheimer's), Rheumatoid arthritis, Osteoporosis, Alcoholic liver disease, B chronic hepatitis, C chronic hepatitis, Steatohepatitis (Absent, Absent – Prior present, Present, Present – New, Present – No Change, Present - Worse)
 - Transient ischemic attack, Venous thromboembolism, Angioedema, New malignant disease (Absent, Present)
 - Previous/current malignant disease (Better, No Change, Worse)

Pharmacological treatment of HF

- ATC level 2 of HF medication at Visit 1, Visit 2 and Visit 3.
- Preferred name of HF medication at Visit 1, Visit 2 and Visit 3.
- Dose and frequency of HF medication
- Duration of HF medication at Visit 1 in groups (≤ 1 year, > 1 year to ≤ 2 years, > 2 year to ≤ 3 years, > 3 years);

NT-proBNP, stability and suitability for prospective interventional period

- NT-proBNP ever tested before Visit 1 (Yes, No)
- NT-proBNP in pg/ml at Visit 1 and Visit 3.
- NT-proBNP in groups (≥ 600 to < 800 pg/ml, ≥ 800 to < 999 pg/ml, ≥ 1000 to < 1200 pg/ml, ≥ 1200 pg/ml) at Visit 1 and Visit 3.
- Absolute Change in NT-proBNP between Visit 1 and Visit 3 (change calculated via *post minus pre value*)
- Clinical stability of the patient at Visit 1 (Yes, No)

[figure not shown]
- Suitability for prospective interventional period of the study (Yes, No)
- Referral to cardiologist (Yes, No)
- Reason for non-referral to cardiologist

[figure not shown]
Cardiologist's advice

- Cardiologist's advice on therapy level (No change, Dose reduction, Dose increase, Discontinuation, New prescription)
- Cardiologist's advice on patient level (No change, Treatment intensification, Treatment reduction, Treatment adaption)
- Implementation of treatment changes by cardiologist (Yes, No, Partially)
- Acceptance of cardiologist's advice by primary care physician on therapy level (Yes, No)
- Acceptance of cardiologist's advice on patient level (All changes implemented, No changes implemented, Changes partially implemented).
- Reason for non-acceptance of the cardiologist's advice

Patient reported outcomes

- EQ-5D VAS at Visit 1, Visit 2, Visit 3, absolute change from Baseline to Visit 2 and Visit 3 and absolute change from Visit 2 to Visit 3 (change calculated via *post minus pre value*).
- EQ-5D utility index at Visit 1, Visit 2, Visit 3, absolute change from Baseline to Visit 2 and Visit 3 and absolute change from Visit 2 to Visit 3 (change calculated via *post minus pre value*).
- EQ-5D single dimensions at Visit 1, Visit 2 and Visit 3.
- KCCQ sub-scores, total symptom score and clinical summary score at Visit 1, Visit 2, Visit 3, absolute change from Baseline to Visit 2 and Visit 3 and absolute change from Visit 2 at Visit 3 (change calculated via *post minus pre value*).

